4.2 Patient enrolment

All patients who provide informed consent must be registered in the electronic data capture (EDC) system including any screen failures. The screening number will be automatically allocated during the process.

Before enrolling the patient in the trial, the Investigator or designated representative must determine the eligibility of the patient. Please ensure that CDD are notified of any eligibility concerns at least four working days before treatment is planned.

CONFIDENTIAL

Eligible patients must be enrolled in the EDC system before they start treatment with vandetanib. If the patient is eligible the patient number will be automatically allocated during the enrolment process.

Dose level allocation will be confirmed to the Investigator (and team as applicable) by the CDD following patient enrolment.

5 TREATMENT

5.1 Selection of the Phase I starting dose and schedule

5.1.1 Selection of Vandetanib dose

Initially vandetanib will be dose loaded at 300 mg od for four days (to rapidly reach the approximate steady state dose of 100 mg od) followed by 10 days at 100 mg od. The dose loading will achieve the steady state plasma concentration at a faster rate than would be possible using 100 mg od tablets. The steady state plasma concentration will then be maintained by dosing once daily with 100 mg.

Dose loading the vandetanib for the first four days of the study is a novel approach which has not been performed in clinical trials using vandetanib before.

In vandetanib monotherapy trials, it was observed that 28 days of 100 mg od administration was required before a steady state of vandetanib was achieved. The length of time to achieve steady state is a concern, especially in the expansion cohort which will recruit NSCLC patients. Disease progression in this group of patients can be rapid. To reduce the time between starting vandetanib and achieving steady state a novel administration schedule has been proposed to reach the steady state of vandetanib within 14 days and allow administration of the combination treatment. The loading dose of 300 mg od vandetanib has been explored in monotherapy trials and has been found to be tolerable to patients (please see current version of vandetanib IB).

The vandetanib dose at steady state is based on the experience of previous clinical trials (refer to the vandetanib IB for detailed summaries of previous trials), which showed acceptable tolerability and safety profile at the selected dose level.

Steady state doses of 200 or 300mg od vandetanib will be considered based on emerging data during the study.

Should the steady state dose of 300mg od be explored, an increased 'loading phase' total dose of vandetanib may be considered i.e. 600mg (300mg bd) for two days before reverting back to 300mg od. This two day 600mg "dose loading" should allow for plasma levels approximating the expected 300mg od steady state level to be reached within a few days thereby reducing the period during which the patient has sub pharmacodynamic plasma levels of Vandetanib. Steady state will therefore be reached within 14 days as in previous cohorts. Pharmacokinetic modelling of the proposed regimens using a 200 or 300 mg dose of vandetanib has been performed and the appropriate loading phase of vandetanib has been established for both doses should a decision be made to increase the vandetanib dose.

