2.2.1.4 Clinical Pharmacokinetics

The PK of vandetanib is linear. The steady state exposure is reached at day 28 with a once-daily dosing. The absorption is slow with a median time to maximum plasma concentration (t_{max}) of 4 to 10 hours. The slow clearance (total plasma clearance after an oral dose (CL/f) of 11 L/h) and the large volume of distribution (3000 L) give a long terminal half-life (t_{1/2}) of about 10 to 19 days. Vandetanib is eliminated both in the faeces and in urine. Therefore, in patients with mild and moderate renal impairment the exposure is increased by about 1.5-fold and by 2-fold in patients with severe renal impairment. Hepatic impairment or food has no effect on exposure. In healthy volunteers, the CYP3A4 inhibitor, itraconazole did not modify the exposure to vandetanib but the CYP3A4 inducer rifampicin significantly reduced by about 40% the exposure to vandetanib.

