2.2.1.5 Safety

The CRUKD/11/001 study will explore a maximum total dose of 300mg with the option of increasing this up to 600mg (300mg bd during the loading phase only) should the safety profile of the combination with selumetinib be acceptable at the lower doses.

Vandetanib has been explored at several doses up to 1200mg od (healthy volunteers) with minimal symptoms. In cancer patients, chronic dosing of 600mg od has resulted in diarrhoea and other AEs.

Vandetanib has a very long half-life for a small molecule meaning that several weeks dosing are required to reach the 300mg od steady state plasma levels. In the CRUKD/11/001 study, a total dose of up to 600mg (as 300mg bd) can be administered at the start of the loading dose phase (Days 1 and 2) before reverting back to a maximum of 300mg od. This two day 600mg “dose loading” should allow plasma levels approximating the 300mg od steady state level to be reached within a few days thereby reducing the period during which the patient has sub pharmacodynamic plasma levels of Vandetanib. Given the extended half life of vandetanib (10-19 days), it is unlikely that two days of 600 mg administration would

result in the severity of toxicity seen in the chronic dosing setting and therefore have any safety impact on patients.

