In addition studies of vandetanib monotherapy occurrences of dyspnoea, pneumonia and interstitial lung disease were reported in some cases CTCAE (version 3.0) Grade ≥ 3 . There is also data from a pharmacoethnicity study suggesting that interstitial lung disease may occur more often in patients from Japan than in patients from elsewhere. Dyspnoea and interstitial lung disease have been reported in patients receiving selumetinib, although the majority of these events have occurred in patients with lung/pleural disease due to their underlying malignancy. The combination of two agents with this finding may result in a higher frequency or intensity of these adverse events.

The gastrointestinal AE's observed with both agents does raise the possibility of an interaction of the combination on the absorption one or both agents. Additionally both vandetanib and selumetinib have been shown to induce CYP3A4 and selumetinib is a substrate of CYP3A4 raising the possibility of metabolic interaction. Pharmacokinetics of both agents and the two most abundant metabolites of each will be performed during the study to detect any such interactions.

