3.1 Clinical trial objectives and endpoints

Primary objectives and endpoints

Primary objectives	Endpoints
Assessing the safety and toxicity profile of the combination of vandetanib and selumetinib.	Determining causality of each adverse event to vandetanib or selumetinib and grading severity according to NCI CTCAE Version 4.02
To propose a recommended dose and schedule for Phase II evaluation of the combination of vandetanib and selumetinib.	Determining the MTD of the combination of vandetanib and selumetinib as proposed by the protocol. OR the single agent recommended Phase II dose (RP2D) of vandetanib in combination with the single agent RP2D of selumetinib.

Secondary objectives and endpoints

Secondary objectives	Endpoint
Determine the plasma PK profiles of vandetanib and selumetinib and their metabolites	PK parameters during Cycle 1 including Cmax and AUC pre and post treatment with vandetanib alone and following the combination of vandetanib and selumetinib. Parameters to be measured include: 
• vandetanib• selumetinib and N-desmethyl metabolite. (other metabolites may be measured as determined during the study).
Expansion cohort To evaluate progression free survival (PFS) of patients with NSCLC after treatment with the combination of vandetanib and selumetinib.	Determine PFS at 12 weeks (from date of first dose of vandetanib) by RECIST (Response Evaluation Criteria In Solid Tumors) criteria.
Expansion cohort To evaluate the survival rate of patients with NSCLC after treatment with the combination of vandetanib and selumetinib.	Determine the one year survival rate.
Expansion cohort To assess the tumour metabolism in patients with NSCLC.	Measurement of tumour metabolism using CT FDG-PET imaging during Cycle 1 pre and post treatment with vandetanib alone and following the combination of vandetanib and selumetinib.

Tertiary objectives and endpoints

Tertiary objectives	Endpoint
[REDACTED]	[REDACTED]

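### The two-day 600 mg vandetanib load gives only a 2–3 day head start, so the claim that 300 mg od reaches steady state within 14 days as in earlier cohorts does not follow from the protocol's own pharmacokinetics

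*Protocol*

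**What the plan says.** Section 2.2.1.4 states "The PK of vandetanib is linear" and "The steady state exposure is reached at day 28 with a once-daily dosing". It gives CL/F 11 L/h, a volume of 3000 L and a terminal half-life of about 10 to 19 days. Section 5.1.1 repeats the time course for the lower dose: "28 days of 100 mg od administration was required before a steady state of vandetanib was achieved". Section 2.2.1.5 says of the higher dose that "several weeks dosing are required to reach the 300mg od steady state plasma levels".

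Cohorts 1–3 shorten this with 300 mg od for four days followed by 100 mg od. If a 300 mg od maintenance dose is explored, section 5.1.1 allows 300 mg bd for two days before 300 mg od. It concludes "Steady state will therefore be reached within 14 days as in previous cohorts", and adds that modelling has been done and a suitable loading phase established for the 200 and 300 mg doses. The output of that modelling is not shown. Section 2.2.1.5 makes a separate statement, that the load "should allow plasma levels approximating the 300mg od steady state level to be reached within a few days".

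Vandetanib is sampled on Days 4, 15 (before the first selumetinib dose) and 29 (section 8.3.1). The secondary endpoint in section 3.1 is "PK parameters during Cycle 1 including Cmax and AUC pre and post treatment with vandetanib alone" and again after the combination. Section 2.3.4 says that pharmacokinetics of both agents "will be performed during the study to detect any such interactions".

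**The concern.** Linear kinetics make the time to steady state independent of dose, so the 28-day figure applies at 300 mg as well as at 100 mg. Bringing that point forward to Day 14 needs a head start of about 14 days. The load that is meant to provide it is, relative to maintenance, a quarter of the one used in Cohorts 1–3, yet the same result is claimed for both.

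The sentence is the stated reason for expecting a 14-day run-in to serve at a tripled maintenance dose. It also tells the reader that vandetanib is level by Day 15. If it is still rising, part of any Day 15 to Day 29 increase is accumulation. That part could be taken for an effect of selumetinib, or could offset a real fall.

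**Working it through.** **Size of the loads, in maintenance doses**
- 300 mg regimen: 2 × (600 − 300) = 600 mg surplus; 600/300 = 2 doses.
- Cohorts 1–3: 4 × (300 − 100) = 800 mg surplus; 800/100 = 8 doses.

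**A bound needing no compartment model.** Assume only linear kinetics and that what remains of a dose falls with time. The two surplus doses are the oldest, so at Day 14 they add at most 2/14, or 14% relative, to the unloaded level.

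**One compartment.** Let t be the half-life and r = 2^(−1/t). As a fraction of steady state, the unloaded trough after n days is 1 − r^n. A surplus of k maintenance doses on day d adds k(1 − r)r^(n−d).

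The stated clearance and volume give t = ln 2 × 3000/11/24 = 7.9 days, so r = 0.916. At Day 14:
- Unloaded: 1 − 0.916^14 = 0.707.
- Cohorts 1–3: 0.707 + 2 × 0.084 × (r^13 + r^12 + r^11 + r^10) = 0.707 + 0.246 = 0.953. Unloaded Day 28 is 0.914, so the 14-day statement is reproduced for these cohorts.
- 300 mg regimen: 0.707 + 0.084 × (r^13 + r^12) = 0.707 + 0.056 = 0.763.
- Equivalent unloaded day: ln(1 − 0.763)/ln(0.916) = 16.4, a head start of 2.4 days. The unloaded Day 28 level is met at 28 − 2.4 = 25.6, that is, Day 26.

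**Other half-lives.** For the 300 mg regimen the head start is 2.55, 2.43, 2.39, 2.32 and 2.16 days at t = 6.5, 7.9, 8.4, 10 and 19 days. For Cohorts 1–3 it is 14 days or more when t is at most about 10.5 days, and 10.3 days at t = 19.

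**Range of models.** The stated facts do not fit one compartment: 7.9 days lies outside 10–19 days, and a 10–19 day half-life puts unloaded Day 28 at only 86–64% of steady state. No percentage defines steady state, so I assumed 90–95% at unloaded Day 28 for models A and C.

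| Assumption | Day 14, 300 mg regimen | Day 14, Cohorts 1–3 | Day 15 to 29 change, 300 mg regimen | Same, Cohorts 1–3 |
|---|---|---|---|---|
| A. One compartment, Day 28 at 90–95% (t = 8.4–6.5 d) | 74–83% | 93–101% | +14 to +21% | −1 to +5% |
| B. One compartment, t = 10–19 d | 68–45% | 86–59% | +27 to +46% | +9 to +26% |
| C. Two compartments, terminal 10–19 d, fast 0.5–3 d, Day 28 at 90–95% | 77–92% | 89–101% | +3 to +17% | −3 to +6% |

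Model C is the weighted sum of two such recursions, with the weight set so that unloaded Day 28 equals 90% or 95%. It is the only one of the three that respects both the 28-day figure and the stated half-life. In every variant of A, B and C, Day 14 of the 300 mg regimen matches unloaded Day 16–17, and the level stays at or above unloaded Day 28 only from about Day 26.

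**The case against.** The strongest defence is that modelling was done and only its output is missing, which is not in itself an error. That is fair, but the modelling could rescue the sentence only by departing from the linearity or the 28-day figure that the protocol states.

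A second defence is that the protocol speaks of approximate steady state and sets no percentage. Under model C, Day 14 can be as high as 92%, only a few points below unloaded Day 28. This stands as a limit on the size of the shortfall. It does not make Day 14 equivalent to Day 28, or to what Cohorts 1–3 achieve.

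Third, little operational depends on the sentence. The 300 mg dose and its load are conditional, and section 5.2.1 has the Sponsor confirm loading and schedule after PK review for every cohort after Cohort 3. Section 13.3 is non-compartmental and sets no interaction threshold. All of this stands and lowers the importance of the point. It has also been argued that the interaction of interest is induction acting on selumetinib. However, section 2.3.4 also raises altered absorption of either agent, so the vandetanib comparison remains relevant.

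A reader might infer that reaching approximate levels within a few days is wrong as well. The documents do not support that: Day 4 is 41–50% of steady state under model A but 50–100% under model C, and in some variants the unloaded Day 28 level is touched briefly that early.

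**Conclusion.** The 14-day sentence in section 5.1.1 does not follow from the protocol's stated kinetics. The head start of about 2–3 days, and Day 26 for lasting attainment of the unloaded Day 28 level, hold in every one- and two-compartment variant tried. The size of the shortfall does not have one value. The most consistent model gives Day 14 at about 77–92% of steady state and a Day 15 to Day 29 rise of about 3–17%. The larger rises in the table come from one-compartment models that contradict either the stated half-life or the 28-day figure.

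Two stronger readings should be resisted. One is to quote 14–21% as the expected drift; it rests on model A alone. The other is to see a safety defect in first-cycle DLTs being observed before full steady state. Under model A, mean exposure over Days 15–42 is already about 90–95% of steady state, and the regimen is used only if the Sponsor selects it after PK review. This is a minor correction to the rationale and to how the PK is read.

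**What to change.** In section 5.1.1, replace the 14-day sentence with the modelled fraction of the 300 mg od steady state at Days 15, 29 and 42, taken from the modelling the protocol says was performed. Alternatively, specify a load which that modelling and tolerability data show meets the 14-day target.

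Add one sentence, in section 5.1.1 or 13.3: for this regimen, the Day 15 versus Day 29 vandetanib comparison is to be read allowing for continuing accumulation.

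Leave the few-days statement in sections 2.2.1.5 and 5.1.1 unless the modelling contradicts it.

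The cost of the first option is wording plus figures the sponsor reports having. It needs no new samples or visits and does not delay escalation, though the regimen will look less favourable than now stated. A different load would change treatment and would need its own tolerability support.

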5.1.2 Selection of Selumetinib dose

The starting dose of selumetinib has been selected as 25 mg bd. The starting dose of 25 mg bd is two dose levels below the highest dose of the Hyd-sulfate capsule form explored in previous clinical trials (refer to the selumetinib Investigator Brochure (IB) for detailed summaries of previous trials), 75 mg bd, which showed an acceptable tolerability and safety profile.

This is the first time the combination of vandetanib and selumetinib will be used in humans. Therefore a reduced starting dose of selumetinib has been selected followed by dose escalation to 50 mg bd and then 75 mg bd. Selumetinib 100 mg od is the recommended dose in combination with erlotinib (EGFR inhibitor) (Study D1532C00004, see current selumetinib IB) therefore once daily administration of selumetinib may be considered on observation of unacceptable toxicity under twice daily administration (see Section 3.2).

5.2 Dosing schedule/treatment schedule

Vandetanib is an orally administered tablet. The vandetanib dose is to be taken once or twice a day.

Selumetinib is an orally administered capsule. The selumetinib dose is to be taken once or twice a day.

Patients should take the correct number of vandetanib tablets and selumetinib capsules at the same time every day. Tablets and capsules are to be taken whole and not split. The vandetanib tablets and selumetinib capsules must be swallowed whole (with water) and not chewed, crushed, dissolved or divided.

Selumetinib should be taken on an empty stomach - no food or drink other than water for 2 hours prior to dosing and 1 hour after dosing. There is no restriction on dosing with food for vandetanib therefore vandetanib and selumetinib should be taken at the same time adhering to those restrictions associated with selumetinib.

5.2.1 Dose escalation phase.

Cohorts 1-3: Vandetanib is being dose loaded for the first four days at 300 mg once daily (od) and then be maintained by dosing once daily with 100 mg. Dose loading of vandetanib will only occur once at the start of Cycle 1, at the beginning of the study treatment. Selumetinib will be administered twice a day (bd). Administration will start after on Day 15 following 14 days of treatment with vandetanib alone. The starting dose will be 25 mg bd administered orally. Cohorts of up to 6 patients will receive escalating doses of selumetinib (25, 50 and 75 mg bd).

Cohorts 1-3: Cycle 1 of treatment (loading dose plus single agent plus combination i.e. Days 1- 42) is as follows:

Day														15-42 (28 days)
1	2	3	4	5	6	7	8	9	10	11	12	13	14	15-42 (28 days)
Vandetanib 300 mg od Loading phase*														Vandetanib (100 mg od)* Selumetinib (25/50/75 mg bd)* (or od dosing, see section 5.3)

Cycle 2 of treatment onwards will consist of combination treatment only as follows:

Day 1- 28
Vandetanib and Selumetinib

There is no loading dose or single agent vandetanib treatment period from Cycle 2 onwards.

For cohorts post Cohort 3: following review of PK and clinical data by the Sponsor and Investigators, the Sponsor will confirm:

- Vandetanib loading and single agent dose and schedule (Cycle 1 only)
- Vandetanib dose and schedule in combination with selumetinib
- Selumetinib dose and schedule

On commencing combination therapy, one cycle will consist of continuous daily dosing for 28 days. There will be no planned interval between cycles.

Patients may continue to receive the combination therapy in the absence of disease progression or unacceptable toxicity. If the patient has not progressed after 6 cycles, they may be treated for further cycles after a formal written request has been made to and written approval received from the Sponsor.

5.2.2 Expansion cohort.

All patients will be dosed according to the RP2D of the combination of vandetanib and selumetinib as established in the dose escalation phase.

Patients may continue to receive the combination therapy in the absence of disease progression or unacceptable toxicity. If the patient has not progressed after 6 cycles, they may be treated for further cycles after a formal written request has been made to the Sponsor and written approval received.

5.3 Dose escalation schedule

In the dose escalation stage of the study, the Sponsor reserves the right to investigate alternative doses of vandetanib and selumetinib in response to emerging safety data. Recruitment into cohorts will follow a “rolling-six” design. Dose assignment for each cohort will be carried out, using all available data, by the Sponsor in conjunction with the CI and PI(s).

If MTD is not reached by the third cohort (100 mg vandetanib and 75 mg selumetinib), based on emerging data from the study,

- Vandetanib loading dose and steady state dose may be increased. Once or twice daily dosing will be considered.
- Once daily selumetinib dosing may be considered if twice daily dosing results in unacceptable toxicity.

Treatment will be continuous for up to 28 days for safety assessment and dose escalation purposes. Up to six patients will be studied at each dose level. Dose delay and reductions will be mandated according to protocol-defined criteria.

Treatment of subsequent patients at each dose level should not begin until the first patient has completed 14 days of single agent vandetanib. Their start of treatment date may be staggered by the Sponsor dependent upon emerging data.

A rolling six design (Sklonik *et al*, 2008) will be used to recruit patients. Three to six evaluable patients will be entered at each dose level for the determination of MTD.

The dose level of selumetinib and vandetanib will be assigned according to the number of patients currently enrolled at the current dose level, the number of DLTs (and any other drug related adverse events) observed at the current dose level and the number of patients enrolled who are at risk of developing a DLT. When sufficient data, as deemed by the Sponsor and (Chief Investigator) CI, are available to assess these, the selumetinib and vandetanib dose level will be assigned according to the following:

If the data is available from a minimum of three patients who have been treated in a cohort and no DLTs have been observed at that dose level for the complete duration of their first cycle, then dose escalation can be considered.

If one DLT has been observed at the current dose level in the first cycle, the dose will remain the same.

If two patients experience a DLT at any dose level during the first cycle, the dose will be de-escalated and the previous dose level will be expanded to include up to 6 patients.

If not all data are available from at least three patients in order to take a decision on dose escalation but an eligible patient is ready to begin treatment, the dose level will remain the same. Up to 6 patients may be enrolled at that dose level.

In the event of two patients experiencing a DLT at the first dose level, the dose level may be de-escalated following discussion of all the relevant toxicity data between the Sponsor and the Study Team, including the Chief Investigator.

Dose escalation meetings will be held to determine if it is safe to escalate the dose to the next level. These reviews will be triggered when sufficient patients have had the opportunity to complete the first cycle of combination treatment.

The safety data including a list of DLTs and all AEs will be reviewed along with all other available data by the Sponsor, CI and PI(s). The decision to dose escalate or expand a cohort will be communicated to all investigator sites by the Sponsor.

It is not anticipated that smaller dose escalations or de-escalations will be employed but would need to be considered if there is a large difference in the number of DLTs in two adjacent dose levels.

Following completion of the dose escalation phase, a review of the data will be performed by the Sponsor (to include review by the Protocol, Safety and Review Board (PSRB) before approval is granted by the Sponsor that the expansion cohort can be opened.

Once the MTD of the combination has been determined the expansion cohort will commence. The MTD determined in this cohort will be the dose level of the combination recommended for Phase II trials.

Expansion cohort.

Up to 30 patients with NSCLC will be enrolled to the expansion cohort. All patients will be treated with the combination of vandetanib and selumetinib. The dose of vandetanib and selumetinib will be the RP2D which will be determined in the dose escalation stage of the study.

